8. STUDY PROCEDURES

8.1 Schedule of Evaluations

For all participants, from the time of reconsenting at the start of study CAB-LA availability (Week 0), there will be study visits every 24 weeks for the duration of their participation.

At the time of writing of this protocol version, the standard of care for both Kenya and Uganda is to offer biomedical prevention as part of the HIV prevention package that includes provision of PrEP for persons at risk of HIV acquisition, such as persons with partners living with HIV or of unknown HIV status, or those with a history of exchange/transactional sex, recent STIs, or recurrent use of PEP (more than 3 times a year). PEP is offered primarily after occupational exposures or in cases of sexual assault. For participants consenting in the extension, in the control arm, they will continue to be seen by government staff in the HIV clinic or other service location, like a drop-in centre, and receive prevention interventions according to standard of care guidelines recommended by the country's Ministry of Health. There will be no change to their HIV prevention healthcare.

Control participants will be seen for a study visit every 24 weeks for HIV testing (RNA and rapid), weight, and a survey on which prevention method(s) they have been using and self-reported risk. If control participants report using medications such as PrEP or PEP at the interim visits, they will be asked to provide hair, blood, or urine samples in order to measure HIV prevention medication levels.

For intervention participants who do not choose CAB-LA, there will be study visits every 12 weeks; however, they can decide to begin CAB-LA at any time during the initial 48-week extension. Participants will not be able to initiate or restart CAB-LA in the additional extension period between Week 48 and Week 96; only those who are taking CAB-LA at the time of the Week 48 visit may continue. Intervention participants that choose CAB-LA will have study visits that align with their injection visits (every 4 weeks for the first two months and then every 8 weeks thereafter), but can return to an alternate DCP intervention if they decide to stop CAB-LA.

For participants that select CAB-LA, the extension visits will also include (Table 6):

- A separate qualitative interview (At time of CAB-LA start, Week 24 and Week 48)
- Safety Labs:
 - HBsAg at baseline
 - ALT at Weeks 0 and 24; optionally at Weeks 8 and 48
- Pregnancy tests
- In addition to the Week 24 and 48 extension visits, injection visits will occur in clinic every 4 weeks for the first two months and then every 8 weeks thereafter
- HIV-RNA Cepheid test at baseline, Week 24, Week 48, Week 72, Week 96
- Plasma will be stored at each visit for future use to evaluate use of alternate HIV assays and cabotegravir PK. Small hair samples will be stored at visit weeks 8, 24, 32, and 48 to assess cabotegravir PK.
- Participants that stop CAB LA prior to the end of the extension time period will continue to be followed in the study but *not* be actively followed beyond the 96 week followup time of the study.

- Oral PrEP (TDF/3TC) will be recommended to cover tail
- Participants will switch back to Q12 week follow-up

Table 5. Schedule of Evaluations Dynamic Choice Prevention Extension – Baseline to Week 48

	Screening/ Baseline	Week 12	Week 24	Week 36	Week 48 ⁴
DCP Intervention (For persons not receiving CAB-LA)¹					
Study visit	X	X	X	X	X
DCP intervention, including:	X	X	X	X	X
- Offer PrEP, PEP, prevention options ²	X	X	X	X	
- HIV testing options	X	X	X	X	X
- Visit location choice	X	X	X	X	X
- Structured assessment of barriers	X	X	X	X	X
- GBV screening	X		X		X
HIV self-test (alternative to rapid)		X	X	X	
Rapid (blood-based) HIV test	X	X	X	X	X
STI symptom screen	X	X	X	X	X
Pregnancy testing (optional)	X	X	X	X	X
DCP (including those persons on CAB-LA) and SOC					
Measure height (baseline only) and weight	X		X		X
Assess self-reported PrEP/PEP use and HIV risk over prior 6 months	X		X		X
Complete Week 24 or 48 Visit eCRF			X		X
Hair sample collection if any PrEP or PEP doses taken in last 30 days			X		X
HIV RNA			X		X
SOC Only					
Study Visit	X		X		X
Referral to standard prevention options	X		X		X
Rapid (blood-based) HIV test	X		X		X
Suspected seroconversion³					

¹Late visits for routine assessments will not be considered Protocol Violations, allowing flexibility during the COVID-19 pandemic

²This assessment will be done on all intervention participants at baseline

³See Figure 2

⁴Week 48 visits may occur between 40 and 56 weeks after Baseline

If CAB-LA is not available in country at the 48-week endpoint, all participants in the intervention arm will have the opportunity to continue on the study until week 96 or until CAB-LA is available in country, whichever occurs first, according to the schedules of evaluation described in Tables 5a and 6. Participants who are currently on CAB-LA at the Week 48 visit may continue on CAB-LA through Week 96. CAB-LA may not be initiated or restarted during the additional 48-week extension to Week 96. Prior to conducting procedures for visits after Week 48, participants in the intervention arm will be reconsented to extend their participation up to Week 96.

Table 5a. Schedule of Evaluations for Extension of Intervention Arm – Week 60 to Week 96

	Week 60	Week 72	Week 84	Week 96 ³
DCP Intervention (For persons not receiving CAB-LA)¹				
Study visit	X	X	X	X
DCP intervention, including:	X	X	X	X
- Offer PrEP, PEP, prevention options ^{2,*}	X	X	X	X
- HIV testing options	X	X	X	X
- Visit location choice	X	X	X	X
- Structured assessment of barriers	X	X	X	X
- GBV screening		X		X
HIV self-test (alternative to rapid)	X	X	X	
Rapid (blood-based) HIV test	X	X	X	X
STI symptom screen	X	X	X	X
Pregnancy testing (optional)	X	X	X	X
Measure weight		X		X
Assess self-reported PrEP/PEP use and HIV risk over prior 6 months		X		X
Complete Week 72 or 96 Visit eCRF		X		X
HIV RNA		X		X
Suspected seroconversion²				

¹Late visits for routine assessments will not be considered Protocol Violations, allowing flexibility during the COVID-19 pandemic or for other outbreaks.

²See Figure 2

³Week 96 visits may occur between 88 and 104 weeks after Baseline

*Participants will not be given the option to initiate or restart CAB-LA after the Week 48 visit; only other prevention options will be available.

Table 6. Schedule of Evaluations for CAB-LA users (weeks indexed by date of initial CAB LA injection) – Baseline to Week 96

	CAB Screening/ Baseline	CAB Week 4	CAB Week 8	CAB Week 16	CAB Week 24	CAB Week 32	CAB Week 40	CAB Week 48 ⁷	CAB Week 56	CAB Week 64	CAB Week 72	CAB Week 80	CAB Week 88	CAB Week 96 ⁷
Measure weight	X				X			X			X			X
CAB LA injection	X	X	X	X	X	X	X	X	X	X	X	X	X	
STI Symptom Screen	X	X	X	X	X	X	X	X	X	X	X	X	X	X
Suspected Seroconversion	X	X	X	X	X	X	X	X	X	X	X	X	X	X
HIV Testing														
-Rapid test (Country std. algorithm)	X	X	X	X	X	X	X	X	X	X	X	X	X	X
-HIV RNA ⁶	X				X			X			X			X
-Stored plasma (2cc) for future HIV testing	X	X	X	X	X	X	X	X	X	X	X	X	X	X
CAB PK														
-Hair sample (if CAB-LA received in last 120 days)			X		X	X		X						
-Stored plasma (from 2 cc sample above)		X	X	X	X	X	X	X						
Safety Labs														
-Pregnancy testing ¹	X	X	X	X	X	X	X	X	X	X	X	X	X	X
-ALT Monitoring ^{4, 5}	X		X*		X			X*			X*			X*
Adverse Event Monitoring	X	X	X	X	X	X	X	X	X	X	X	X	X	X
GBV Screening	X				X			X			X			X
Survey and IDI														
-Participant CAB-LA Survey and IDI ²	X				X			X						
-Provider and Clinic Staff DCP-LA Survey and IDI	X				X			X						
Costing³	X	X				X								
For participants who stop CAB LA before end of extension study														
-For 48 weeks from last injection: Recommend oral PrEP (TDF/3TC) to cover tail														
-Switch back to Q12 week visits - HIV RNA and pregnancy testing Q12 weeks														

¹For women who become pregnant, repeat pregnancy tests are not needed. Women who become pregnant during the study will be followed to delivery for assessment of mother and infant status

²Participant survey/IDI will be conducted at start of CAB-LA and Weeks 24 and 48 from time of CAB-LA start or discontinuation.

³Costing will occur between weeks 24-48.

⁴ALT Monitoring will occur at baseline, Week 24 for all participants. *Per provider discretion, ALT monitoring will occur at Weeks 8, 48, 72 and 96.

⁵Bilirubin and additional labs indicated will be tested in the case of ALT increase.

⁶HIV RNA will be drawn at CAB-LA reinduction, as described in Table 6.

⁷Week 48 visits may occur between 40 and 56 weeks after Baseline; Week 96 visits may occur between 88 and 104 weeks after Baseline; only participants on CAB-LA at the Week 48 visit may take CAB-LA between weeks 48 and 96.

9. INFORMED CONSENT

9.1 Informed Consent Process

All participants in the DCP trials will be offered participation in the CAB-LA Extension. Consent forms will be translated from the original English to the language(s) spoken in the community. The consent form will be read to participants in their local language. Participants who agree to take part and sign the consent form will continue in the study. In this consent, women will be informed about the risks and benefits of CAB-LA during pregnancy and breastfeeding. In the case that participants become pregnant while using CAB-LA, they will be asked for an additional re-consent to follow-up for ascertainment of pregnancy and infant outcomes.

Participants will remain in the randomization arm they were assigned to at their initial DCP visit in Phase A. Participants in the SOC arm will consent to return for two additional follow-up visits at weeks 24 and 48 following re-consent for the CAB-LA extension. Intervention participants that do not choose CAB-LA will consent to continue the quarterly study visits and Intervention participants that choose CAB-LA will have study visits that align with their injection visits (every 4 weeks for the first two months and then every 8-weeks thereafter). Intervention participants will have flexibility to switch between PrEP, PEP, and CAB-LA. Unlimited switches between biomedical prevention options, including between CAB-LA and oral, will continue to be permitted during the extension, both to reflect participant choice and to bridge planned missed doses of CAB-LA. Clients and providers will discuss options for prevention and risk during regular visits and interim visits, in addition to continuous provider trainings on offering choice and refreshers for clients. Changes in prevention choices will be documented in study eCRF forms, which will include the CAB-LA option. DCP intervention participants that choose the CAB-LA option will be informed about the visit schedule, side effects, and risks and benefits, before consenting. If CAB-LA becomes available via the Ministry of Health during the trial, persons in the control arm will be eligible as per standard of care.

9.2 Assent Process

Participants aged 15-17 years old who meet the definition of ‘mature or emancipated minors’ as set by the Uganda National Council for Science and Technology and Kenya MoH can participate in these studies and will be consented on the adult participant consent forms. Participants aged 15-17 that do not meet the definition of ‘mature or emancipated minors’ may participate with parental co-signature. All participants will be asked to re-consent for the CAB-LA extension.

9.3. Documentation of Informed Consent

Documentation of written informed consent and verbal consent will be recorded on informed consent logs for all study activities. The logs will contain the participant’s study ID, clinic ID, initials, name, language of consent used, and whether the individual signed the document or provided a fingerprint in the case of written consents, or verbally affirmed their consent in the case of verbal consents.

9.4 Stored Samples and Associated Data Considerations

Plasma samples will be collected and stored for retrospective HIV testing and PK.

Hair samples collected from participants on PrEP, CAB-LA or PEP in the extension will be collected and stored for later measurements of HIV-prevention drug levels, which will be conducted at the UCSF Hair Analytical Lab in the United States.

Blood samples from persons who acquire HIV in Phase A prevention trials will be stored for additional testing for HIV diagnostics (if indicated) and HIV drug resistance. Testing will be performed in-country when available (e.g. standard genotyping for HIV drug resistance). Specialized research assays for diagnostic and resistance testing (e.g. next-generation sequencing) will be performed at the University of Pittsburgh [name] Lab in the United States. Blood and urine samples will be stored for testing CAB-LA/PrEP/PEP drug levels performed at the UCSF Hair Analytical Lab in the United States.

Specimens may be held up to five years in order to complete HIV diagnostics, resistance, or PK tests as outlined in this protocol. The study may hold specimens to test in batches at later time since these tests are being performed solely for research, not for clinical care, or for a biobank for future use. Specimens will be destroyed after tests are performed.

All other biological samples collected during the study will be tested shortly after collection and any remaining specimen discarded.

10. SAFETY ASSESSMENT OVERVIEW

10.1 Cabotegravir (GSK1265744A) Injectable Suspension- for intramuscular use: Product information

- a. CAB-LA will be supplied by the ViiV Healthcare Limited Pharmaceutical Company
- b. **Indications and Usage.** CAB-LA is indicated in at-risk adults and adolescents weighing at least 35 kg for pre-exposure prophylaxis (PrEP) to reduce the risk of sexually acquired HIV-1 infection. Individuals must have a negative HIV-1 test prior to initiating CAB-LA. CAB-LA will not be used as a supplement for PEP.

10.2 Administration Overview.

- a. CAB-LA will be offered as direct to inject only (no oral lead-in)
- b. Injection: Single-dose vial containing 600 mg/3 mL (200 mg/mL) of cabotegravir is a white to light pink, free-flowing, extended-release injectable suspension
- c. CAB-LA will be administered by trained healthcare staff by gluteal intramuscular injection only. Body Mass Index will be considered to ensure appropriate needle

length is sufficient to reach the gluteal muscle.

- d. Study participants will be tested for HIV infection prior to initiating CAB-LA, and with each subsequent injection of CAB-LA, including HIV RNA testing (Cepheid).
- e. Prior to starting CAB-LA, healthcare staff will counsel study participants about the importance of adherence to scheduled dosing visits to help reduce the risk of acquiring HIV infection and development of resistance.

10.3 Pharmacy

- a. The study sponsor, UCSF, will receive CAB-LA directly from ViiV Healthcare and distribute to the country pharmacies per country study drug shipping procedures
- b. In-country pharmacists will receive and log the CAB-LA per country procedure and detailed in the CAB-LA Pharmacy SOPs
- c. As described in 6c below, CAB-LA will be stored at 2°C to 30°C (36°F to 86°F) at clinic sites; proper storage and handling will be monitored by in-country pharmacy teams and validated by accountability logs and other source documents
- d. Details on these procedures are outlined in the Standard Operating Procedures.
 - i. CABPHARM-01 Study Drug Ordering and Acquisition
 - ii. CABPHARM-02 Study Drug Accountability
 - iii. CABPHARM-03 Study Drug Storage
 - iv. CABPHARM-04 Dispensing and Administration of Study Drug
 - v. CABPHARM-05 Disposition and Destruction of Study Drug
 - vi. CABPHARM-06 Communication and Dissemination of Information to the Study Pharmacist

10.4 Injection Dosing

- a. The initial injection dose of CAB-LA is a single 600-mg (3-mL) intramuscular injection of CAB-LA given 4-weeks apart for 2 consecutive times
- b. After the 2 initiation injection doses given consecutively 4-weeks apart, the continuation injection dose of CAB-LA will be a single 600-mg (3-mL) intramuscular injection of CAB-LA, every 8-weeks.
- c. There is a +/- 7 day window for before or after the date the participant is scheduled to receive their next injection

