Participants in the control arm can access biomedical HIV prevention interventions (oral PrEP, PEP) through the local health clinics. They will have access to CAB LA when it becomes available through the Ministry of Health. Participants in the intervention arm will have access to PrEP, PEP + CAB LA with the additional structured dynamic choice support described above. Intervention participants that choose not to use CAB-LA will continue on a quarterly study visit schedule, per the standard DCP Intervention study schedule. Intervention participants that choose CAB-LA will be seen once every 4 weeks for the first two injections, then every 8-weeks for injections and study visits. Should participants stop CAB-LA, they will revert to the quarterly DCP visit schedule. All participants will be seen for mid-point and end-point visits every 24 weeks.

A subset of participants that use CAB-LA (up to 40) will be asked to complete an in-depth-interview and all participants will take a survey at Weeks 0, 24, and 48 (or at CAB-LA discontinuation) for researchers to better understand participant's experience with CAB-LA and to improve delivery as it becomes more widely available. A subset of 10 providers will also be asked to complete an in-depth interview and all providers will complete surveys at their Weeks 0, 24, and 48 of administering CAB-LA. These interviews and surveys will help researchers understand better ways to deliver CAB-LA, as it becomes more widely available. Participants that seroconvert (acquire HIV during the trial) will also be asked to participate in an in-depth interview, as it will help researchers understand transmission and ways to improve DCP delivery in future implementation.

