10.5 Missed Doses

Study staff will provide adherence support to CAB-LA participants. When doses are missed, study staff will follow the applicable guidelines. Providers will work pro-actively and prospectively identify periods during which participants are likely to miss doses (eg travel). Participants will be provided with oral bridging prevention medication (TDF-FTC) to cover these periods. Upon return to clinic for planned or unplanned missed doses, CAB-LA dosing will be as per protocol below.

- a. If a scheduled injection visit is missed or delayed by more than 7 days, the study

clinician will determine when resumption is appropriate.

b. Recommended Dosing after a missed visit is detailed in **Table 7**.

Table 7. Missed Dosage Recommendations

Time since Last Injection	Recommendation
If second injection is missed and time since first injection is:	
Less than or equal to 8-weeks	Administer 600-mg (3-mL) gluteal intramuscular injection of CAB-LA as soon as possible, then continue to follow the every 8-weeks injection dosing schedule.
Greater than 8-weeks	Restart with 600-mg (3-mL) gluteal intramuscular injection of CAB-LA, followed by a second 600-mg (3-mL) initiation injection 4-weeks later. Then continue to follow the every 8-weeks injection dosing schedule thereafter.
If third or subsequent injection is missed and time since prior injection is:	
Less than or equal to 12 weeks	Administer 600-mg (3-mL) intramuscular injection of CAB-LA as soon as possible, then continue with the every 8-weeks injection dosing schedule.
Greater than 12-weeks	Restart with 600-mg (3-mL) gluteal intramuscular injection of CAB-LA, followed by the second 600-mg (3-mL) initiation injection dose 4-weeks later. Then continue with the every 8-weeks injection dosing schedule thereafter.

10.6 Contraindications. CAB-LA is contraindicated in individuals:

- a. With unknown or positive HIV-1 status
- b. With previous hypersensitivity reaction to cabotegravir
- c. Receiving the following co-administered drugs for which significant decreases in cabotegravir plasma concentrations may occur due to uridine diphosphate glucuronosyltransferase:
 - vii. Anticonvulsants: Carbamazepine, oxcarbazepine, phenobarbital, phenytoin
 - viii. Antimycobacterials: Rifampin, rifapentine

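### Table 6 and Section 10.4 put the third CAB-LA injection at different weeks (8 versus 12), nothing says which governs, and the hair PK plan fits only Table 6

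*Protocol*

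**What the plan says.** **Two initiation doses, then 8-weekly.** Section 10.4 says: "After the 2 initiation injection doses given consecutively 4-weeks apart, the continuation injection dose of CAB-LA will be a single 600-mg (3-mL) intramuscular injection", and the sentence goes on to set an 8-week spacing. The Protocol Summary (Section 3) has CAB-LA users "seen once every 4 weeks for the first two injections, then every 8-weeks for injections and study visits". Table 7 in Section 10.5 uses the same pattern for re-induction: a restart dose, "followed by a second 600-mg (3-mL) initiation injection 4-weeks later", then 8-weekly.

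**A third dose at Week 8.** Table 6 is titled "Schedule of Evaluations for CAB-LA users (weeks indexed by date of initial CAB LA injection". Its injection row marks Baseline and Weeks 4, 8, 16, 24, 32, 40, 48, 56, 64, 72, 80 and 88, and it has no Week 12 column. Section 8.1 says that "injection visits will occur in clinic every 4 weeks for the first two months and then every 8 weeks thereafter", and Section 9.1 says "every 4 weeks for the first two months and then every 8-weeks thereafter". That wording fits Table 6, though it could be read as Weeks 0 and 4 only.

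**The window.** Section 10.4 states: "There is a +/- 7 day window for before or after the date the participant is scheduled to receive their next injection". Section 10.5 applies "If a scheduled injection visit is missed or delayed by more than 7 days".

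**What depends on the calendar.** Section 21.2 collects hair at Weeks 8, 24, 32 and 48 after CAB-LA start. It treats hair as taken before injections when correlating hair and plasma levels at the end of the dosing interval. The Implementation row of Table 4 measures fidelity as the proportion of providers offering CAB-LA on the appropriate schedule, without saying which schedule that is.

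**The concern.** A study drug should have one dosing calendar. Here two are given, and neither the protocol nor the SAP says which controls.

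A site that gives the third dose on the Section 10.4 date is 28 days late by Table 6 and meets the Section 10.5 condition for a delayed visit. A site that gives it on the Table 6 date is 28 days early by Section 10.4, and Section 10.5 covers only missed or delayed doses. Staff who follow either text correctly can be recorded as off schedule under the other.

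Two secondary analyses are also exposed. The fidelity measure has two possible standards for the third injection, or for every later one if it is scored by nominal week. If Section 10.4 governs and hair is still taken at the nominal weeks, the end-of-interval correlation in Section 21.2 would use mid-interval hair.

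**Working it through.** **Inputs.** Injection weeks from the Table 6 row; the dosing rule and window from Section 10.4; hair weeks from Sections 8.1 and 21.2; the Week 48 visit window (40-56 weeks) from Table 6, footnote 7; the coverage rule (starts 3 days after an injection, continues 67 days) from SAP Section 3.1.

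**1. Is Table 6 read correctly?** The injection row is an unbroken run of 13 marks, with only Week 96 blank. The hair row, read by the same columns, gives Weeks 8, 24, 32 and 48, as Sections 8.1 and 21.2 say in prose. The column alignment is therefore sound.

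**2. Does Section 10.4 reproduce Table 6?** Weeks 0 and 4, then 8 weeks after each previous dose, gives 4 + 8 = 12, then 20, 28 and so on. It does not. Two other readings do reproduce Table 6: counting the first 8 weeks from dose 1, or giving three doses 4 weeks apart. The first leaves only 4 weeks between the second initiation dose and the first continuation dose. The second contradicts the stated two initiation doses.

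**3. The two calendars compared.**

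| | Table 6 | Section 10.4 |
|---|---|---|
| Injection weeks | 0, 4, 8, 16, 24, 32, 40, 48, 56, 64, 72, 80, 88 | 0, 4, 12, 20, 28, 36, 44, 52, 60, 68, 76, 84, 92 |
| Gaps (weeks) | 4, 4, 8, 8, ... | 4, 8, 8, 8, ... |
| Doses before Week 48 | 7 | 7 |
| Doses through Week 48 | 8 | 7 |
| Doses through Week 96 | 13 | 13 |

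Only Weeks 0 and 4 are common. One interval differs: second to third dose, 28 versus 56 days. That single shift carries forward, so the nth dose is 28 days apart for every n from 3 on.

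**4. Third-dose windows.** Table 6: Day 8 × 7 = 56, ± 7, gives Days 49-63. Section 10.4: Day 12 × 7 = 84, ± 7, gives Days 77-91. The gap between them is 77 − 63 = 14 days.

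**5. Hair samples: weeks since the previous dose.**

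| Hair week | Table 6 | Section 10.4 |
|---|---|---|
| 8 | 4 of 4 | 4 of 8 |
| 24 | 8 of 8 | 4 of 8 |
| 32 | 8 of 8 | 4 of 8 |
| 48 | 8 of 8 | 4 of 8 |

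Under Table 6, all four fall on an injection visit. Under Section 10.4, none does: each is 28 days after a dose (21-35 days if that dose was within 7 days of its nominal date) in a 56-day interval. Section 21.2 takes 1 cm of hair as one month, so the proximal 0.5 cm would reflect roughly weeks 2-4 of the interval instead of weeks 6-8. The 40-56 week window could realign only the Week 48 sample, to the Week 44 or Week 52 injection.

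**6. Primary endpoint.** The longest scheduled gap on either calendar is 56 days. Coverage from the previous dose lasts at least to Day 67 after it, and coverage from the next begins on Day 56 + 3 = 59. There is no break after Day 3. Scheduled coverage over 48 weeks is (336 − 3)/336 = 333/336 = 99.1% on both.

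**The case against.** The best case is that the intended calendar can be inferred. Section 10.4 is the dosing section and names exactly two initiation doses, whereas Table 6 is a schedule of evaluations. Table 7 supports this: it tolerates a second injection up to 8 weeks after the first, and a third or later one up to 12 weeks after the previous. If each limit is the due interval plus 4 weeks, the third dose is treated as an 8-week dose. This makes Section 10.4 the likelier intent. It does not remove the conflict, because Sections 8.1 and 9.1 and the hair weeks lean the other way.

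A second point is that Week 12 is derived, not printed: Section 10.4 does not name the start of its 8-week clock. That is true, but counting from dose 1 goes against the Protocol Summary, which limits 4-weekly spacing to the first two injections.

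Third, the hair problem is conditional. Visits for CAB-LA users are meant to align with injections, so hair sampling could move with them. This stands: mid-interval sampling follows only if sites keep to the nominal weeks. Even then the printed hair weeks would need correcting.

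Fourth, the practical harm is limited. A third dose 8 weeks after the second is within Table 7's 12-week limit and needs no re-induction. Section 10.5 leaves delayed doses to the clinician, and the pharmacy SOPs listed in Section 10.3 may settle the matter. These points lower the stakes. The SOPs are not among these documents, and they would not correct the protocol itself.

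**Conclusion.** The concern holds: this is an internal inconsistency in a dosing rule. The calendars differ in one interval (28 versus 56 days between the second and third injections), the third-dose windows do not overlap, and no text sets precedence. The hair plan agrees with injection visits at 4 of 4 nominal weeks under Table 6 and 0 of 4 under Section 10.4.

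This rests on counting the 8-week interval in Section 10.4 from the second dose. The hair consequence also assumes sampling at the nominal weeks. The effect on fidelity is confined to the third injection unless it is scored by nominal week.

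Not affected are the primary coverage endpoint (taken from injection logs, with the same scheduled coverage), power, and plasma PK (drawn before each injection). The point should be fixed, but it does not threaten the trial's main comparison.

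**What to change.** State one governing injection calendar and make Table 6, Sections 3, 8.1, 9.1 and 10.4, and Table 7 agree with it. The sponsor must decide which.

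- **If Section 10.4 governs** (the more natural reading of the dosing text), move the Table 6 injection columns after Week 4 to Weeks 12, 20, 28 and so on, and tie hair sampling to injection visits.
- **If Table 6 governs**, add the third 4-weekly dose to Sections 3 and 10.4 and to Table 7.

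In either case, score fidelity by interval since the last injection with the 7-day window, and use actual time since last injection in the PK analysis in place of nominal week.

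The cost is a protocol clarification and a site memo. No procedures or participants are added, and no new data are needed because injection dates are already logged.
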